### Specific objectives

*Primary objective: To assess the decline in cognitive function using standardized neurocognitive assessment in patients with atrial fibrillation over the age of 60 years with CHA2DS2-VASc score  $\geq 2$  treated with Apixaban versus warfarin*

Our hypothesis is that Apixaban is associated with reduction in decline of cognitive function scores when compared to dose adjusted warfarin with goal INR of 2 – 3. We will test this hypothesis by randomizing patients with AF over the age of 60 years and CHA2DS2-VASc score  $\geq 2$  to anticoagulation with Apixaban vs Warfarin. The primary endpoint of this study is the longitudinal change in cognitive function scores over a follow-up of 2 years in individual cognitive domains (executive, language, memory and visuospatial) and global cognitive function. The development of mild cognitive impairment or dementia will also be assessed as a secondary end point. By the end of this study it is our expectation that the risk of cognitive impairment in AF patients taking Apixaban compared to Warfarin will be well defined and such results will provide a novel measure to reduce the burden of cognitive impairment in AF.

**Rationale:** Cognitive function scores are chosen as the primary end point due to their sensitivity to detect changes in cognitive function within a short span of time. While dementia is also an important end point, it is increasingly recognized that milder degrees of cognitive dysfunction are more prevalent and may have an important impact on a person's quality of life and morbidity. Early recognition of cognitive decline can lead to earlier intervention to either treat or prevent progression. Hence the primary end point of decline in cognitive function in one or more domains will be a clinically relevant and a patient centered outcome.

*Secondary objective: To determine the incidence of new cerebral infarct and new cerebral microbleeds using cerebral MRI in AF patients treated with Apixaban vs warfarin.*

The secondary objective is to evaluate the impact of Apixaban on subclinical emboli and CMBs detected by brain MRI compared to Warfarin. Our hypothesis is that Apixaban is associated with fewer new subclinical emboli and CMBs, compared to warfarin. This has important clinical implications as reduction in these has significant potential to reduce the risk of cognitive impairment.

**Rationale:** There is growing evidence of the important relationship between subclinical emboli and cerebral microbleeds (CMBs) and the development of cognitive impairment. These MRI findings can be viewed as 'bio-markers' of risk of future cognitive decline.

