## 1 PROTOCOL SUMMARY

### 1.1 SYNOPSIS

Title:	Randomized trial of Apixaban vs dose adjusted Warfarin in reducing rate of cognitive function decline, silent cerebral infarcts and cerebral microbleeds in non-valvular atrial fibrillation (NVAF) patients with CHA2DS2-VaSc score $\geq 2$ .
Study Description:	This study is a randomized clinical trial of patients with AF, whose CHA2DS2-VaSc score $\geq 2$ , it will compare Apixaban vs dose adjusted warfarin on the rate of cognitive function decline, silent cerebral infarction and cerebral microbleed. Our hypothesis is that, anticoagulation with Apixaban reduces the rate of decline in cognitive function, when compared to Warfarin and that Apixaban reduces cognitive decline by reducing the rate of new cerebral infarction and cerebral microbleeds detected by cerebral MRI compared to warfarin.
Objectives:	
Primary Objective: Assess the difference in decline in cognitive function using standardized neurocognitive assessment in AF patients treated with Apixaban vs Warfarin.
 
Secondary Objectives: Assess the difference in incident mild cognitive impairment or dementia in NVAF patients treated with Apixaban vs Warfarin. Assess the difference in development of new silent cerebral infarcts and cerebral microbleeds on brain magnetic resonance imaging (MRI) in NVAF treated with Apixaban vs Warfarin.

Endpoints:	
Primary Endpoint: The individual cognitive domain and global cognitive function score in NVAF patients treated with Apixaban vs Warfarin
 
Secondary Endpoints: (1) New mild cognitive impairment or dementia; (2) new cerebral infarcts on brain MRI and (3) new cerebral microbleeds on brain MRI in NVAF treated with Apixaban vs Warfarin.

Study Population:	Patients (male and female over the age of 60 years) diagnosed with NVAF over the age of 60 years with a CHA2DS2-VASc score $\geq 2$ , who have never been treated with Apixaban , or prior treatment with Apixaban <1 month.
Phase:	3
Description of Sites/Facilities Enrolling Participants:	Mayo Clinic, Rochester
Description of Study Intervention:	Apixaban 5 mg twice daily unless patient has any 2 of the following: Age $\geq 80$ years, body weight $\leq 60$ kg, or serum creatinine $\geq 1.5$ mg/dL, then reduce dose to

2.5 mg twice daily.

[figure not shown]

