### 3 OBJECTIVES AND ENDPOINTS

OBJECTIVES	ENDPOINTS	JUSTIFICATION FOR ENDPOINTS
Primary		

To assess the change in global cognitive function using standardized neurocognitive assessment in patients with atrial fibrillation over the age of 60 years with CHA2DS2-VASc score <math>\geq 2</math> treated with Apixaban versus warfarin
	
The individual cognitive domain and global cognitive function score using a battery of standardized neurocognitive function tests (presented below in detail).
 
 
○ All enrolled subjects will undergo assessment of cognitive function at (1) before or within 1 month of randomization (2) 1 year and (3) 2 years.
 
	
Cognitive function scores are chosen as the primary end point due to their sensitivity to detect changes in cognitive function within a short span of time. While dementia is also an important end point, it is increasingly recognized that milder degrees of cognitive dysfunction are more prevalent and may have an important impact on a person’s quality of life and morbidity. Early recognition of cognitive decline can lead to earlier intervention to either treat or prevent progression. Hence the primary end point of decline in cognitive function in one or more domains will be a clinically relevant and a patient centered outcome.
 
Additionally, AF may have a greater impact on non-memory cognitive domains such as executive function, thus predisposing to non-amnesic dementia. Hence we will test individual cognitive domains to

OBJECTIVES	ENDPOINTS	JUSTIFICATION FOR ENDPOINTS
		increase the sensitivity of the tests.
Secondary		

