***Measurement of primary endpoint: The individual cognitive domain and global cognitive function score***

All enrolled subjects will undergo assessment of cognitive function at (1) enrollment, (2) 1 year and (3) 2 years.

AF may have a greater impact on non-memory cognitive domains such as executive function, thus predisposing to non-amnesic dementia. Hence we will test individual cognitive domains to increase the sensitivity of the tests.

The following standardized tests will be administered at each visit by a trained neuropsychometrist.

Testing of four major cognitive function domains

1. Executive function - Trail Making Test B and Digit Symbol Substitution Test
2. Language - Boston Naming Test and Category Fluency
3. Memory - Logical Memory-II (delayed recall), Visual Reproduction-II (delayed recall) and Auditory Verbal Learning Test (delayed recall)
4. Visuospatial - Picture Completion and Block Design

Questionnaires to rule out competing diagnoses:

1. The Beck Depression Inventory
2. The Beck Anxiety Inventory

An informant, identified by the subject as someone with whom they have contact at least once every week, will be interviewed in person or by telephone to complete the following:

1. Clinical dementia rating scale (CDR)
2. Functional assessment questionnaire

For patients lost to clinic follow-up, assessment of cognitive state will be performed using the following questionnaires administered over the telephone:

Telephone interview of cognitive status (TICS-M) (administered to subject)

2. Clinical dementia rating scale (administered to informant)
3. Functional assessment questionnaire (administered to informant)

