## 9 STATISTICAL CONSIDERATIONS

### 9.1 STATISTICAL HYPOTHESES

- Primary Efficacy Endpoint:

Treatment with Apixaban is associated with reduced rate of decline in global cognitive function score compared to treatment with Warfarin in AF patients  $\geq 60$  years of age and CHA2DS2-VaSC score  $\geq 2$ .

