## 9.2 SAMPLE SIZE DETERMINATION

Sample size calculation is based on the primary endpoint, the rate of decline in the global cognitive function score. The sample size calculations are based on data from the Mayo Clinic Study of Aging which has enrolled community dwelling individuals to perform the same battery of neurocognitive tests proposed in this study. We investigated the rate of decline in the global cognitive function score in (1) patients with and without AF and (2) in AF patients on warfarin vs. not on warfarin. The Mayo Clinic Study of Aging (MCSA) has identified a significant decline in the individual and global cognitive function scores in patients with AF compared to those without AF. In addition, the rate of decline was similar in AF patients treated with warfarin and those not treated with warfarin. The observed rate of decline in global cognitive score in AF patients on warfarin was -0.12 / year (SD 0.16). A reduction in the rate of decline in the global cognition function score of 0.05/year with Apixaban compared to Warfarin was considered clinically relevant. We used R to calculate power as a single sided test of superiority of Apixaban over Warfarin. A sample size of 140 in each arm is required to achieve >80% power to detect

the difference stated assuming an alpha error of 0.05. Assuming a screen failure rate of 20%, a total of 175 will be accrued in each arm.

Enrollment will be age and gender stratified with goal of enrolling >50% patients over the age of 70 years in whom the risk of cognitive decline is greater. Recruitment of the required number of subjects will be feasible given the high volume of AF patients in the local community and those seeking care for AF at the Mayo Clinic. For example, 5000 individuals developed incident (new onset) AF in Olmsted county alone after the year 2000. The rate of prevalent AF is higher in this population. The other 7 counties from which participants will be recruited have similar population demographics and prevalence of AF. We anticipate that we will be able to recruit the required number of subjects in the first year of the study.

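### The primary endpoint is five scores in some sections and the global score alone in others, with no testing order; if any one could count, the false-positive rate would be about 9–20% rather than 5%

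*Combined protocol and SAP*

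**What the plan says.** Five places make the four domain scores and the global score primary together:

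- Synopsis (1.1), primary endpoint: "The individual cognitive domain and global cognitive function score in NVAF patients treated with Apixaban vs Warfarin".
- Section 3, endpoint column: "The individual cognitive domain and global cognitive function score using a battery of standardized neurocognitive function tests".
- Section 4.1, primary objective: "The primary endpoint of this study is the longitudinal change in cognitive function scores over a follow-up of 2 years in individual cognitive domains". The sentence goes on to name executive, language, memory and visuospatial function and then adds global function.
- Section 8.1, and again under 9.1, as a heading: "Measurement of primary endpoint: The individual cognitive domain and global cognitive function score".

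Three places use the global score alone:

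- Section 3, objective column of the same table row: "To assess the change in global cognitive function using standardized neurocognitive assessment".
- Section 9.1, the one formal primary hypothesis: "Treatment with Apixaban is associated with reduced rate of decline in global cognitive function score compared to treatment with Warfarin in AF patients".
- Section 9.2: "Sample size calculation is based on the primary endpoint, the rate of decline in the global cognitive function score". The test is one-sided ("We used R to calculate power as a single sided test of superiority of Apixaban over Warfarin") at an alpha of 0.05.

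Section 9.4.1 fits a linear mixed model to each score. It gives no deciding score, testing order, test level or multiplicity rule, and no other section supplies one. Its list of scores includes attention, which is not a scored domain, where Sections 4.1, 8.1 and 9.1 have executive function.

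**The concern.** The plan has to settle in advance which result makes this phase 3 trial positive, and the text allows more than one answer. A report claiming success on executive function alone, with a null global score, could cite Section 4.1 for calling that a primary endpoint result. A report claiming success only on the global score could cite 9.1 and 9.2. The rationale text in Sections 3 and 4.1 adds to the difficulty by describing the primary endpoint as decline in at least one domain.

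The two readings have different error rates, and the power statement in 9.2 covers only the global score. The participants, the principal investigator and the coordinator know the treatment assignment (Section 6.3), which is a further reason not to leave the choice until results are known.

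**Working it through.** **1. The plan's own figure.** Inputs from Section 9.2: difference 0.05 per year, SD 0.16, 140 per arm, one-sided alpha 0.05.

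- Standard error of the difference = 0.16 × √(2/140) = 0.0191.
- Noncentrality = 0.05 / 0.0191 = 2.61.
- Power (noncentral t, 278 df) = 83.2%. The normal approximation, Φ(2.61 − 1.645), gives 83.4%.

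The claim of more than 80% power is reproduced, for the global score only.

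**2. False-positive rate if any of the five scores could count.** Section 9.1 derives the global score as the average of the four domain scores, so the five tests are not independent. Five independent tests would give 1 − 0.95⁵ = 22.6%, which does not apply here.

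The calculation draws four equally correlated standard normal domain statistics under no treatment effect, and takes the global statistic as their standardised mean:

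Z_global = (Z₁ + Z₂ + Z₃ + Z₄) / (4 × √[(1 + 3r)/4])

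Equal variances and a common correlation r are assumptions. The documents give no value for r, so a range is shown. Each row uses 2,000,000 draws (Monte Carlo standard error at most 0.0003).

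| r | Global score alone > 1.645 | Any of five > 1.645 | A domain positive, global not | Any of five > 1.960 |
|---|---|---|---|---|
| 0 | 5.0% | 19.7% | 14.7% | 10.5% |
| 0.3 | 5.0% | 16.7% | 11.7% | 9.0% |
| 0.5 | 5.0% | 14.6% | 9.5% | 8.0% |
| 0.7 | 5.0% | 12.0% | 7.1% | 6.6% |
| 0.8 | 5.0% | 10.6% | 5.6% | 5.7% |
| 0.9 | 5.0% | 8.8% | 3.8% | 4.7% |

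The fourth column is the part that the ambiguity adds: a domain is falsely positive although the global score is not. The last column uses one-sided 0.025 per score, because Section 9.4.1 states no level; the comparator there is 2.5%.

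**3. Power under two ways of resolving it.**

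- Five co-equal primary scores with Bonferroni, 0.05/5 = 0.01 each: power for the global score at 140 per arm falls to 60.9% (noncentral t). By the normal approximation, 206 per arm would be needed for 80%.
- Global score first, domains after it: the global score keeps the full 0.05, so power stays at 83.2% with 140 per arm.

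**The case against.** The strongest reply is that the statistical sections already choose. The only formal primary hypothesis (9.1) and the only stated alpha (9.2) concern the global score, and 9.2 calls the decline in that score the primary endpoint. Much of the contrary text is headings and table cells describing what is measured. No sentence says that one positive score is enough, and the rationale about decline in at least one domain can be read as describing patients rather than a rule for trial success. This stands in part: on that reading the error rate is 5%, and the higher figures are conditional. It does not remove the conflict, because Section 4.1 defines the primary endpoint in a full sentence as all five scores, and 9.4.1 does not carry the 9.1 choice through.

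A second point is that Section 4.1 joins the scores with *and*, so a reader could require all five to succeed. The same simulation then gives a false-positive rate of about 0.3% at r = 0.5 and 2.2% at r = 0.9, and the difficulty becomes lost power. This is correct. It is a third reading, and it strengthens the case for naming one endpoint.

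Third, the range depends on assumptions. The 19.7% end needs unrelated domains, and 8.8% is not a floor, since the rate approaches 5% as r approaches 1. That is accepted.

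Fourth, the sponsor wants domain tests because AF may affect non-memory domains more, and a prespecified alpha split would also be valid. Bonferroni is a conservative comparator because it ignores the correlation. Both points are fair. Domain testing can stay; it needs a stated rank.

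The attention/executive mismatch is a slip in wording and carries no weight in the error-rate argument.

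**Conclusion.** The concern holds. The current text contradicts itself on the primary endpoint, including within one row of the Section 3 table and within Section 9.1, and no rule elsewhere resolves it. As written, a lone positive domain could be reported as a primary result.

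The size depends on the reading. With the global score alone, the one-sided error rate is 5% and power is 83%. If any of the five may count at one-sided 0.05, the error rate is about 9–20% for r from 0.9 down to 0, and about 12–17% for r between 0.7 and 0.3. At one-sided 0.025 it is 4.7–10.5% against 2.5%. These ranges rest on the equal-correlation structure and on values of r that are not in the documents. The inconsistency and the missing hierarchy do not depend on those assumptions. This should be corrected before results are known.

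**What to change.** - In the synopsis and Sections 3, 4.1, 8.1, 9.1 and 9.4.1, name one primary endpoint: the treatment difference in rate of change of the global cognitive function score over 2 years.
- In 9.4.1, state that the treatment-by-time term for the global score is the primary test, at the level used in 9.2.
- Make the four domain scores secondary. Test them only if the global score succeeds, with one prespecified multiplicity procedure, for example Holm.
- Reword the rationale in Sections 3 and 4.1 so that decline in a single domain is not described as the primary endpoint.
- Separately, in 9.4.1, replace attention with executive function.

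The cost is text changes in six places. No new data and no extra participants are needed, and power for the global score stays at 83%. The Statement of Compliance requires IRB approval before an amendment takes effect. The one real loss is that a positive result in a single domain could no longer be claimed as success on the primary endpoint.

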## 4.2 JUSTIFICATION FOR DOSE

Drug dosing will be in compliance with FDA approved recommendations. There will be NO off-label use of drugs.

### **Apixaban**

5 mg twice daily unless patient has any 2 of the following: Age  $\geq 80$  years, body weight  $\leq 60$  kg, or serum creatinine  $\geq 1.5$  mg/dL, then reduce dose to 2.5 mg twice daily.

Further dose adjustment will be performed in special circumstances as per FDA approved Apixaban drug label as follows:

For patients qualifying for Apixaban 5 mg twice daily, the dose of Apixaban will be decreased by 50% when co-administered with drugs that are strong dual inhibitors of CYP3A4 and P-gp (e.g., ketoconazole, itraconazole, ritonavir, or clarithromycin).

### **Warfarin**

Dose adjusted to maintain INR between 2 – 3. Dose adjustment performed using a standardized nomogram at an anti-coagulation clinic will be encouraged but not required. Interval of INR testing will be determined by the treating physician.

## **4.3 END OF STUDY DEFINITION**

A participant is considered to have completed the study if he or she has completed all phases of the study including the last visit or the last scheduled procedure shown in the Schedule of Activities (SoA), Section 1.3.

The end of the study is defined as completion of the last visit or procedure shown in the SoA in the trial globally.

## **5 STUDY POPULATION**

### **5.1 INCLUSION CRITERIA**

In order to be eligible to participate in this study, an individual must meet all of the following criteria:

1. Patients diagnosed with atrial fibrillation based on electrocardiographic documentation
2. Male or female greater than or equal to the age of 60 years,
3. Have a CHA2DS2-VASc score  $\geq 2$
4. Have never been treated with Apixaban, or prior treatment with Apixaban <1 month.
  
5. Provision of signed and dated informed consent form
6. Stated willingness to comply with all study procedures and availability for the duration of the study
7. Ability to take oral medication and be willing to adhere to the study intervention regimen

### **5.2 EXCLUSION CRITERIA**

An individual who meets any of the following criteria will be excluded from participation in this study:

1. Patients who are not a candidate for oral anticoagulation as assessed by a treating physician including the presence of active bleeding.
2. Prior treatment with Apixaban for >1 month. (Prior exposure to warfarin or novel direct oral anticoagulants other than Apixaban is not an exclusion criterion).
3. Known hypersensitivity to warfarin or Apixaban.
4. CHA2DS2-VASc score <2

5. Valvular AF defined as history of rheumatic valve disease, moderate or greater mitral stenosis, and presence of a mechanical cardiac valve.
6. Need for dual anti-platelet therapy with aspirin and another agent such as a thienopyridine.
7. Aspirin monotherapy with doses > 100 mg if the patient is unable to reduce the dose to <100 mg.
8. Severe renal insufficiency (serum creatinine level of >2.5 mg/dl or calculated creatinine clearance of <25 ml/minute) or dialysis.
9. Prior severe bleeding including intracranial hemorrhage and GI bleed requiring transfusion.
10. Recent stroke (within 7 d)
11. Known diagnosis of dementia or dementia diagnosed at first evaluation.
12. Presence of MRI non-compatible implanted devices including cardiac implantable electronic devices. Patients with MRI conditioned cardiac implantable electronic devices will also be excluded. This is done in light of concerns regarding patient safety in MRI scanner.
13. Inability to undergo MRI due to claustrophobia.
14. Current or expected systemic treatment with strong dual inducers of CYP3A4 and P-gp (e.g., rifampin, carbamazepine, phenytoin, St. John's wort) because such drugs will decrease exposure to apixaban
15. Current or expected systemic treatment with strong dual inhibitors of CYP3A4 and P-glycoprotein (e.g., ketoconazole, itraconazole, ritonavir, or clarithromycin) in patients who would qualify for Apixaban dose of 2.5 mg BID.
16. Currently enrolled in another investigational device or drug trial that has not completed the primary endpoint or that clinically interferes with the current study endpoints.
17. Co-morbid condition(s) that could limit the subject's ability to participate in the trial or to comply with follow-up requirements, or that could impact the scientific integrity of the trial.
18. Prisoners or subjects who are involuntarily incarcerated. Subjects who are compulsorily detained for treatment of either a psychiatric or physical (e.g., infectious disease) illness.
19. Severe comorbid condition with life expectancy  $\leq 1$  y
20. Active alcohol or drug abuse or psychosocial reasons that make study participation impractical.

